## **AIMS & HYPOTHESES FOR RANDOMIZED, WAITLIST-CONTROL STUDY.**

**Aim #1. To assess whether SafelyYou Guardian + HIL will lower fall rates.** Hypothesis 1. Compared to standard-of-care (waitlist control group), SafelyYou Guardian will reduce fall rates in study participant over the study period of 6 months.

**Aim #2. To assess how use of the SafelyYou Guardian affects time spent on the ground after a fall.** Longer time to fall discovery is associated with higher human suffering and often leads to higher medical morbidity/mortality. Hypothesis 2: SafelyYou Guardian + HIL will reduce time to fall discovery (time from fall to staff notification) to under 5 minutes and reduce time spent on the ground to under 15 minutes. Since there is no way to measure control participants time spend on the ground, the aim will not have a comparison but will be descriptive.

**Aim #3. To assess whether SafelyYou Guardian will lead to improvement in hard clinical outcomes.** Hypothesis 3: SafelyYou Guardian participants will lower ED visits and hospitalizations when compared to control. This reduction in ED and hospitalization will correlate with reduced fall rates (aim #1) and reduced time spent on the ground (aim #2). We will review the strength of the association with aim #1 and #2 outcomes.

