For aim #3, we will ascertain the occurrence of fall in the intervention group by doing follow-up case review of each detected fall. For the control group, we perform biweekly check with facility staff and family regarding knowledge and documentation of any falls. For falls in both the intervention and control group, we will additional collected data regarding occurrence of ED visit and hospitalization days. We will also include occurrence (or absence) of any operations, intensive care unit stays, and other medical procedures. We will also collect mortality data.

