#### **Data collection:**

Demographic and clinical data set: We collect demographic data including age, gender, race/ethnicity, primary clinical diagnoses for SNF stay with specific focus on dementia subtype, most recent orthopedic surgery (<3 months) or reason for hospitalization, chronic medical conditions (top 3), and baseline medications (number of medications). Beyond the data collected from the video, data specific to the falls is collected either by direct extraction from the platform or from incident reports kept by facilities as (State regulations require facility track and file incident reports for all known falls). For the control population, the time of unwitnessed falls is unknown, but the number of falls and ER visits is collected from the existing facility incident reports. For the population equipped with SafelyYou Guardian, we will have direct access to the time of the fall, the time it took the HIL to verify the fall and call the facility, and the time on the ground. Note that for the residents with SafelyYou Guardian, we expect these values to be in increments of minutes.

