#### Clinical outcomes.

For Aim #1, the primary outcomes are the number of falls detected by facilities using the adverse incident reporting system as per routine facility protocol. While use of video detected falls will be used in the intervention group to assist with prevention of future falls, we will not use this as the actual outcome measure: is not the standard-of-care, and the control group will not have video recorded outcomes. There is a bias for detecting falls using video since existing fall reporting systems do not capture falls which staff do not know about (e.g., when a resident is able to get back in bed after a fall). Staff-detected falls which automatically trigger adverse incident reporting is the “real-world” outcome measure and current stand-of-care. Thus, outcomes will differ by facility (each facility has different adverse incident reporting operations and implementation, hence the randomization at each facility will adjust for such variables).

Aim #2 will be a naturalistic observation of SafelyYou Guardian with HIL for 6 months. Specifically, for all the facilities, the use of the SafelyYou Guardian enables direct notification of falls to front-line staff in the facilities, by intervention of the HIL. We can directly measure time on the ground for the residents as follows: (1) The time of the fall is recorded by

SafelyYou Guardian (which detected it); (2) The time of intervention of the front-line staff is logged by the staff after finding the residents on the ground. This means that for the population with treatment, we can directly measure the time of fall discovery (successful call leading to front line staff intervention), and time on the ground (since time of the intervention is logged by the facility). This is because time on the ground for monitored residents can be measured precisely by video recording. Reduction of the time on the ground can be computed given the difference between the two.

Aim #3 will include number of ER visits and number of hospitalizations. We will obtain information about resident demographics, medical comorbidities, emergency room visits, and hospitalization data by asking the study participant legal representatives. In addition, we will have participant / participant Durable Power of Attorney complete HIPAA consent forms for release of medical records when indicated if the details of data are not available.

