Following the sample size for a time-averaged response methodology laid out in Fitzmaurice et al., we adjusted the total number of centers needed by a factor related to the number of observed months, anticipated participants per center (30% of 35 participants per center with 10% dropout) and the correlation between measurement months. The dropout rate was roughly at ~1% per month so a 10% dropout over 6 months is a conservative estimate. We assumed an extremely conservative estimate of the correlation between time points (months) of 0.8 and 6 months of follow-up. Reproducible R code is available at <https://github.com/[name]/>. We estimate that a total sample size of 460 ( $n=230/\text{arm}$ ) out of 19 facilities will be needed for a power of 80% to detect a 30% reduction in falls in the intervention group vs. control. Our approach of focusing on estimation and uncertainty and accepting the sample size collected for the main study, is congruent with experts' recommendations stating that the purpose of economic evaluation is not hypothesis testing; given there is no hypothesis testing, there is no requirement for a separate sample size calculation. For Aim 2, we will use similar descriptive statistics as described in Aim 1. For Aim 3, We will use a multivariate regression model to examine predictors of the main outcome, ER visits and hospitalizations (binary variable), using time to fall discovery by staff and time spent on the ground as the main predictors while controlling for baseline participant characteristics and facility characteristics.

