## **Risk/Benefit Assessment**

Minimal risk for study participants is expected as the system does not physically interact with study participants in any way and only provides supplementary support while all existing safety protocols in the facility remain in place.

Risks and/or discomforts include loss of privacy by placing a camera in the private room. Although the system is designed to keep video only when a fall is detected, false alarms do occur which can cause video to be uploaded at any time. If subjects feel uncomfortable about privacy once the cameras are installed, they may withdraw from the study at any time.

The research study personnel take several steps to protect the privacy of each participant. The recorded video does not have audio capability in order to protect private communication of residents and their visitors. Physical signs are posted visibly at the entrance to all private rooms containing cameras. The signs state that video recording is in progress to ensure all visitors and staff entering the room are aware of the camera. Cameras are placed in the private bedroom only, not in the private bathroom. Cameras record video only when an event is detected. Video (with no audio) will be reviewed by the research study personnel after collection. If more than one resident occupies a room, all roommates must provide informed consent for any to participate. All data is encrypted in transit and at rest.

Installation of the wall-mounted cameras will require inserting screws into the wall in the corner of the room adjacent to the ceiling and installing cabling which may be visible. No other risk of property damage is expected.

The ongoing safety procedures at the facility will remain in place.

The SafelyYou system has demonstrated reduced fall risk and unnecessary emergency room visits for those using it in previous studies with under 100 residents enrolled and hundreds more that have used it as a commercial product. We believe the system will provide significant benefits through faster response times to safety-critical situations, help staff make informed decisions about the need for transfer to the emergency room following unwitnessed falls, and reduce the overall frequency of falls through improved root cause analysis to minimize the risk of repeat falls, but this is active research, and we do not know if any of these benefits will occur for certain.

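### Aim 3 has no stated analysis comparing ER visits and hospitalizations between arms: its only model uses a yes/no outcome and predictors that controls lack

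*Combined protocol and SAP*

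**What the plan says.** Aim 3 is introduced under Aims & Hypotheses as "To assess whether SafelyYou Guardian will lead to improvement in hard clinical outcomes". Hypothesis 3 is a contrast between arms: intervention "participants will lower ED visits and hospitalizations when compared to control". A second part of the same aim asks how strongly any reduction is associated with fall rates and time on the ground.

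The outcome and its data appear in several forms:

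- Clinical outcomes, Aim 3 paragraph: "Aim #3 will include number of ER visits and number of hospitalizations", that is, two counts.
- Data collection, for controls: "the number of falls and ER visits is collected from the existing facility incident reports".
- Design, for falls in both groups: "we will additional collected data regarding occurrence of ED visit and hospitalization days", which for ED visits reads as yes/no per fall.
- Data analysis paragraph: a multivariate regression will "examine predictors of the main outcome, ER visits and hospitalizations (binary variable"), with the two time variables as main predictors, adjusted for participant and facility characteristics.

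The Design section also says: "We will also include occurrence (or absence) of any operations, intensive care unit stays, and other medical procedures". Mortality is collected as well. The Risk/Benefit Assessment expects the system to "help staff make informed decisions about the need for transfer to the emergency room following unwitnessed falls", and the Purpose section makes a similar point about avoidable ER visits.

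**The concern.** The stated hypothesis and the stated analysis do not meet. Hypothesis 3 needs a comparison by randomised arm of how often residents go to the ER and how often they are admitted. The model in the Data analysis paragraph asks whether slower discovery and longer time on the ground predict an ER visit or admission. That can serve the second part of Aim 3, but not the first. With no arm comparison specified in advance, its unit, outcome coding, follow-up window and model would all be chosen after the data are seen.

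The binary coding matters too if it is carried over to an arm comparison. Per resident, one visit would equal four visits and an admission, and a resident who dies early without a visit would score as a good outcome. If the two components are pooled, the result could be driven by ER transfer. That is a decision made by unblinded staff and one the video is meant to inform, so a fall in transfers need not mean better health.

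**Working it through.** **1. Can the stated model test Hypothesis 3?** The test needs an arm term, and the model names none. Its main predictors are the two time variables. Aim 2 says that time on the ground cannot be measured in controls. Data collection says that the time of unwitnessed falls is unknown for them, so time to discovery is missing as well. Waitlist residents yield these times only in their second 6 months, when they have the system and no untreated group remains. The model can therefore be fitted only to falls in monitored residents.

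**2. The plan's own figure.** Aim 3 has no sample size. The only one is for Aim 1: 460 residents for 80% power to detect a 30% reduction in falls. No alpha is stated. On the log rate ratio, n per arm = (z_α + z_β)² (1/λ₁ + 1/λ₂) / (ln 0.7)² × (1 + 5 × 0.8)/6.

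- Two-sided 5%, λ₁ = 0.49 × exp(0.467²/2) = 0.546, no dropout inflation: 274.2 × 0.833 = 228.5, a total of 458.
- One-sided 5%, λ₁ = 0.49, divided by 0.9: 223.0 per arm, a total of 448.

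Both are within 3% of 460. Two-sided with dropout gives 508 or 568. So 460 is reachable, but only under choices the plan does not state. It says nothing about power for Aim 3.

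**3. Per-resident reading: information kept.** The inputs are 0.49 falls per month, so 0.49 × 6 = 2.94 per resident, and an assumed share p of falls that lead to an ER visit. Then μ = 2.94p. Relative to the count, any/none keeps μ/(e^μ − 1) of the information on the log rate if counts are Poisson, and 1/(1 + μ) if they are negative binomial with dispersion 1.

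| p (assumed) | μ | Residents with ≥1 visit (Poisson) | Kept, Poisson | Kept, dispersion 1 |
|---|---|---|---|---|
| 5% | 0.147 | 14% | 93% | 87% |
| 10% | 0.294 | 25% | 86% | 77% |
| 20% | 0.588 | 44% | 73% | 63% |
| 30% | 0.882 | 59% | 62% | 53% |
| 50% | 1.47 | 77% | 44% | 40% |

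Power for a 30% reduction, two-sided 5%, with 230 × 0.9 = 207 completers per arm (Poisson), count against yes/no: 43% against 39% at p = 10%; 71% against 61% at 20%; 87% against 73% at 30%.

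**4. Per-fall reading.** With at most one ER visit per fall, yes/no is the whole ER outcome and nothing is lost. But suppose the system prevents 30% of falls and the ER share per fall stays at 20%. The per-fall outcome is then 20% in both arms, while visits per resident drop from 2.94 × 0.2 = 0.588 to 2.94 × 0.7 × 0.2 = 0.412. The benefit that Aim 1 seeks would not show.

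**5. Pooled reading, if compared by arm.** Assume p = 20%, all admissions pass through the ER, ER visits fall by 37% (borrowed from the pilot's reduction in EMS use for falls), and admissions do not change. Any event is then 1 − e^(−0.588) = 44.5% in controls and 1 − e^(−0.588 × 0.63) = 31.0% in the intervention arm. Power at 207 per arm is about 81%, although hospitalization is the same in both arms. At p = 10% and 30% the power is 57% and 90%.

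**The case against.** The sponsor can fairly say that the quoted sentence is a predictor model, not the arm comparison. Its predictors are measured per fall, ED visits are recorded as occurrence per fall, and for that purpose a binary outcome is natural and costs nothing. This stands. The information loss in step 3 applies only to a per-resident reading, rests on an assumed ER share, and is small if visits are rare. It would also be smaller for hospitalizations if they are rarer; the documents give no rate for them either.

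Pooling is an inference. The singular main outcome points to one combined variable, but two separate indicators are possible.

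A reader might infer that the plan would claim better hard outcomes on fewer transfers alone. The documents do not support that: a model without an arm term cannot produce the claim. The hard-outcome label comes from the title of Aim 3, not from the yes/no coding, and would remain with counts. Reduced transfer is also openly stated as an intended benefit.

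A reader might also infer that operations, ICU stays and deaths go unanalysed. The Data analysis paragraph promises descriptive statistics for all variables. That sentence sits in the Aim 1 text and commits to no table of these items by arm, so what is missing is a stated comparison by arm.

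Lastly, admissions can follow from transfers, so hospitalization is not fully independent of the staff decision. That is a reason to report the other outcomes beside it. None of these arguments supplies an analysis for Hypothesis 3.

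**Conclusion.** The concern holds in this form: Hypothesis 3 has no stated analysis. That follows from the text alone and needs no assumption. The mismatch between two counts as defined and a binary variable as analysed, with no unit given, is also plain.

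The size of the coding problem is conditional. Per resident, yes/no keeps about 93% down to 44% of the Poisson information over an assumed ER share of 5% to 50% (87% down to 40% with dispersion 1), counting fall-related visits at the plan's control fall rate. Per fall, no ER information is lost, but prevented falls drop out of view. The risk that an ER-only change passes as a change in both outcomes arises only if the pooled variable is used in an arm comparison. This should be corrected before analysis.

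**What to change.** In the Data analysis paragraph, separate the two questions of Aim 3.

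- **Hypothesis 3.** Compare ER visits and hospitalizations separately, by randomised arm, over the first 6 months. Use per-resident counts in a Poisson or negative binomial mixed model with a facility effect and an offset for days alive and in follow-up.
- **Interpretation.** Describe ER visits as health-care use. Beside them, report hospitalization days, operations, ICU stays and deaths by arm.
- **Association question.** Keep the model with time to discovery and time on the ground as a separate exploratory analysis, per fall, in monitored residents only, with falls clustered within resident. State whether its binary outcome is one composite or two indicators.

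The cost is new SAP wording and a few more tables, with no new data. The downside is two results instead of one, and a narrower claim if only ER visits fall.

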### Design

For Aim 1, we plan to recruit 460 study participants from 19 memory care facilities. For the purpose of this study, facilities will include Skilled Nursing Facilities (SNFs), or equivalent. Aim 1 will be a randomized controlled study using a waitlist control group. The randomization will occur at the individual (resident) level within each facility to control for variations at each facility in terms of facility size, facility administration, and staff training. During the first 6 months, n=230 will receive the intervention (SafelyYou Guardian, i.e. real-time alarms through a phone call from the HIL to the facility, front line staff intervention, and OT review), and n=230 will not receive the intervention. This design is the most rigorous way to test the intervention against the control: the randomization allows for control of confounding variables and has been previously used in the evaluation of medications, non-pharmacological, and mobile electronic interventions (where use of placebo treatment and blinding is not feasible) [87-89]. Previous work used a baseline as control, allowing possible confounding variables. As we recognize that 50% of the interested participants will not receive the intervention, those residents will be offered the intervention for a 6-month extension period (in order to accomplish Aim 2). This is the best compromise between the need for a rigorous randomized controlled trial vs. ethical responsibility to maximize benefit to each study participant.

For Aim #2, we will measure response times to each fall and the amount of time a resident spends on the ground after each fall. We intend to include all 460 participants' data from Aim #1. These will be participants who receive the initial intervention (n=230) and the additional participants who are on the waitlist control group who will receive the intervention in the second 6month period. The design for Aim #2 is observational in nature. The significance is that a large cohort of video data about the naturalistic progression of falls in residents with dementia has never been conducted to our knowledge. We will determine if the two time variables (time to fall discovery by staff and time spent on the ground after a fall, controlling

for baseline participant characteristics – i.e., demographics and medical conditions) and facility size, will predict need for ER visits or hospitalizations.

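### Hypothesis 3 claims fewer ED visits and hospitalizations than control, but the only Aim 3 model has no arm term and needs times that untreated controls do not have

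*Combined protocol and SAP*

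**What the plan says.** The Aims section states Hypothesis 3 as a comparison: "SafelyYou Guardian participants will lower ED visits and hospitalizations when compared to control". It then adds a second, associational goal: "We will review the strength of the association with aim #1 and #2 outcomes".

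The Design section collects events in both groups: "For falls in both the intervention and control group, we will additional collected data regarding occurrence of ED visit and hospitalization days".

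The data analysis text under Clinical outcomes gives one model for Aim 3. It is a multivariate regression of ER visits and hospitalizations, treated as binary, "using time to fall discovery by staff and time spent on the ground as the main predictors", with baseline participant and facility covariates. The Design section describes much the same model under Aim 2, asking whether the two times "will predict need for ER visits or hospitalizations", and calls that design observational. The Poisson mixed model is named only for the outcomes of an Aim 1a.

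On whether the two times exist outside treatment, Aim 2 begins its explanation for having no comparison with "Since there is no way to measure control participants time spend on the ground". Data collection says that when an unwitnessed control fall happened is not known. Clinical outcomes describes direct measurement of both times for treated residents.

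**The concern.** The hypothesis and the analysis answer different questions. The hypothesis asks whether residents randomised to the system have fewer ED visits and hospitalizations than residents randomised to wait. The model asks whether, among falls with recorded times, longer times go with more ED visits or admissions.

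The second question is legitimate, and Aim 3 also asks it. But its answer is confounded by how severe the fall was and by facility response. It is also conditional on having fallen, an event after randomisation that Hypothesis 1 expects treatment to change. It cannot stand in for the first question.

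At stake is one of the trial's three hypotheses, on the outcomes the plan itself treats as the clinically decisive ones. If the comparison is left undefined until data are in hand, the outcome form, event definition, population and period would all be open to choice after the fact.

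**Working it through.** **1. The plan's own figure.** The only sample size is 460 (230 per arm), for a 30% reduction in falls. One reading reproduces it. Take a monthly control rate of 0.49 × exp(0.467²/2) = 0.546, two-sided 5% (assumed) and 80% power. Then n per arm = (1.960 + 0.842)² × (1/0.546 + 1/0.383) / (ln 0.7)² = 274. Multiplying by the time-averaging factor (1 + 5 × 0.8)/6 = 0.833 gives 228.5, so a total of 458. Other readings give other totals. No power or sample size is stated for Aim 3.

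**2. Who can enter the Aim 3 model.** A resident needs a fall with both times recorded.
- Months 1 to 6, intervention arm: eligible if they fall under monitoring.
- Months 1 to 6, control arm: no time on the ground for any fall, so none can enter.
- Months 7 to 12: the Aim 2 design adds the "additional participants who are on the waitlist control group who will receive the intervention in the second 6month period". They enter only once treated.

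So in the randomised period arm does not vary within the model. After crossover both randomised groups contribute, but there is still no untreated comparison. An arm term could not estimate the Hypothesis 3 effect in either case.

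**3. How many residents that is.** From the documents: 0.49 falls per month, 30% reduction, 10% dropout over 6 months, 230 per arm. Assumed: dropout spread evenly, 6 monitored months each, every fall timed, and counts between Poisson and negative binomial with k = 0.5.
- Mean follow-up: 6 × (1 − 0.10/2) = 5.7 months.
- Mean monitored falls: 0.49 × 0.7 × 5.7 = 1.955.
- P(at least one fall): Poisson 1 − exp(−1.955) = 0.858; negative binomial 1 − (1 + 1.955/0.5)^(−0.5) = 0.549.
- First period: 230 × 0.549 = 126 to 230 × 0.858 = 197.
- Waitlist residents entering the second period: 230 × 0.9 = 207, adding 114 to 178.
- Total: 240 to 375 of 460, or 52 to 82%. Untreated controls: 0.

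**4. Precision of the missing contrast, fall-related ED visits.** Expected control falls: 230 × 0.49 × 5.7 = 642. The documents give no share of falls leading to an ED visit, so q = 5 to 30% is assumed. The rate ratio is set at 0.63, from the pilot's 37% reduction in EMS use for falls.

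SE(log RR) = √[φ(1/Ec + 1/Ei)], where Ec and Ei are expected visits in the control and intervention arms. For the negative binomial it is √[1/Ec + 1/Ei + 2/(230 × 0.5)]. Power at two-sided 5%:

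| q | Visits, control vs intervention | Poisson | Neg. binomial, k = 0.5 | Twice Poisson variance |
|---|---|---|---|---|
| 5% | 32 vs 20 | 37% | 31% | 21% |
| 10% | 64 vs 40 | 63% | 49% | 37% |
| 20% | 128 vs 81 | 90% | 66% | 63% |
| 30% | 193 vs 121 | 98% | 75% | 81% |

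At q = 10% the expected 95% CI is 0.43–0.93, 0.39–1.01 or 0.36–1.10 respectively.

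**5. All-cause ED visits.** If half of control visits were fall-related (assumed), the ratio is 0.5 × 0.63 + 0.5 = 0.815, with 64 to 385 control visits. Power is 20 to 77% (Poisson), 15 to 27% (negative binomial, k = 0.5) or 12 to 48% (twice Poisson variance). For hospitalizations the documents give nothing to compute from.

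**The case against.** The best defence is that the contrast is intended, only not written out. Hypothesis 3 states it, fall-linked events are collected in both groups, control ER visits come from incident reports, and the model lists main predictors without expressly excluding arm. The Aim 1a label is never defined, so it is weak evidence of a deliberate limit. This stands as far as intention goes: what is missing is a specified analysis. It does not rescue the model that is specified, because controls lack its main predictors.

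A second point is priority. Only the Aim 1 falls outcome is called primary, and the sample size is for falls. That is true, and it limits the damage, but it leaves a stated hypothesis without an analysis.

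Third, the figures are soft.
- Participant recruitment and retention suggests that the intervention arm may continue for a further 6 months. With a mean of 12 × 0.9 = 10.8 monitored months in that arm, the usable total becomes about 264 to 402 (57 to 87%).
- Cameras cover bedrooms only. If 70% of falls were on camera (assumed), the total is about 211 to 326. Video also finds falls that staff miss, which works the other way.
- The 0.63 ratio comes from uncontrolled pilots and concerns EMS use. At 0.80, Poisson power is about 13 to 54%.

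All of this is fair. None of it changes the count of untreated controls, which is zero.

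Fourth, the case review and biweekly check in the Design section are ways of finding falls, while Clinical outcomes gives one route, through legal representatives and records, for ED and hospital data. That is correct. But if events are attached to falls, a difference in how falls are found carries through to the event counts.

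**Conclusion.** The concern holds, with high confidence. The specified Aim 3 analysis cannot estimate whether the system lowers ED visits or hospitalizations against control, and adding an arm term to it would not help. This follows from the plan's own statements about what can be measured and does not depend on any assumed figure.

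The estimate of 52 to 82% of residents usable rests on the follow-up, camera-coverage and count-distribution assumptions above. The power and interval figures rest also on an assumed ED share and a borrowed rate ratio. They show only that the missing contrast could be anywhere from informative to imprecise, and that it is weaker for all-cause events.

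This should be corrected before data collection, because unequal ascertainment cannot be repaired afterwards. Randomisation, the Aim 1 analysis and the falls sample size are not affected.

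**What to change.** Make the main Aim 3 analysis an intention-to-treat comparison by randomised arm, covering all randomised residents over the first 6 months, for ED visits and separately for hospitalizations. Model counts per resident with a log follow-up offset, a facility effect and allowance for overdispersion; negative binomial is one suitable choice. As no power is stated, report each rate ratio as an estimate with a 95% CI.

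Before data collection, settle three things.
- **Event definition.** Design and Data collection tie ED data to falls and incident reports, while Clinical outcomes sets no such limit. State whether events are fall-related or all-cause; the choice is the sponsor's.
- **Outcome form and unit.** Clinical outcomes gives counts and the Aim 3 model a binary variable. State which applies, and whether the unit is the fall or the resident.
- **Ascertainment.** Use the same method in both arms. At present the intervention arm has case review of each detected fall, whereas "For the control group, we perform biweekly check with facility staff and family regarding knowledge and documentation of any falls".

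Keep the regression on discovery time and time on the ground as exploratory, restricted to monitored falls, with a resident random effect.

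The cost is one more model and some SAP wording. For fall-related events, most of the data are already to be collected. For all-cause events, incident reports are not enough and a per-resident query is needed in both arms; the plan already names legal representatives and record release as sources. The main drawback is that the estimate may be imprecise, more so for all-cause events.
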